1.0 Objectives / Specific Aims

- Objectives: To determine the feasibility and safety of using this assistive device, TheraBracelet, every day during waking hours, and to determine if TheraBracelet's instant effects are sustained during prolonged use.
- Design: Community-dwelling chronic stroke survivors will be randomly assigned to either the treatment or control condition for the first month, followed by a 2-week washout period and then crossover to the other condition. In both the treatment and control conditions, participants will be instructed to wear the device for at least 8 hours/day every day during their normal daily activity and come to the laboratory for evaluation prior to and each week of using the device (for a total of 5 evaluations over 4 weeks). The device will deliver vibration (treatment) or no vibration (control). Double-blinding will be possible because the treatment vibration is imperceptible (i.e., subthreshold).
- Primary Aim: Determine the feasibility and safety of using TheraBracelet daily for a month. For feasibility, compliance in using the device will be assessed by weekly self-reports of usage. Hypothesis: TheraBracelet will have a feasibility level comparable to wearing a non-vibrating wristband. To determine safety, participants will be examined at each weekly visit for any worsening of hand sensation, dexterity, grip strength, upper limb pain, spasticity, and wrist skin irritation. Adverse events will be recorded and categorized by severity (minor, moderate, and serious) and device relevance (related to device use or not). Adverse event frequency will be compared between conditions, and with a comparable FDA-approved device, Bioness electrical muscle stimulator. Hypothesis: TheraBracelet will have a safety level equivalent to or better than the comparable FDA-approved assistive device.

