- For the secondary outcome of durability of TheraBracelet’s instant effect, the hypothesis will be tested using repeated measures ANOVA for each hand function measure, with factors of vibration (on/off), condition (treatment/control), evaluation time (1-5), and their interactions. A significant main effect of vibration, with improved hand function with vibration on vs. off, with non-significant interactions of vibration×evaluation time and vibration×condition, would indicate durability over a month. In contrast, a lesser extent or abolishment of the instant effect toward the later evaluations or for the treatment condition, with significant interactions of vibration×evaluation time or vibration×condition, would indicate desensitization. In that case, the time point at which the instant effect wanes will be examined using Tukey type posthoc pairwise comparisons.
- A possibility exists that instant enhancement of hand function with TheraBracelet may trigger more use of the affected hand in daily living, which, when accumulated over time, might lead to improvement of the innate hand function (without vibration). This is analogous to cane users who may walk more with canes than without, and thus build greater lower limb abilities over time. Thus, change in the innate hand function will be examined. A significant effect of condition×evaluation time, with greater improvement of the innate hand function for the treatment vs. control, will suggest a therapeutic effect of TheraBracelet for secondary investigation.
- Impact of TheraBracelet on activities of daily living and quality of life will be assessed using repeated measures ANOVA for the SIS and SS-QoL, with the main effect of condition.

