- Power analysis: The sample size for the primary outcome of safety was determined for testing hypothesis of non-inferiority using a 2×2 crossover at 80% power and 5% significance level. A sample size of 24 (12 in each condition at randomization) provides sufficient power to conclude non-inferiority within a difference in adverse events of 20% between the discordant pairs (those who are safe with control but unsafe with treatment vs. those with the opposite), assuming a total of 10% discordance rate (proportion of participants with different responses for the two conditions) and a 90% safe rate for the control. That is, we will be powered to statistically conclude non-inferiority (hence safety) if 3 or less out of 24 participants have adverse events in treatment vs. control. For the Secondary Aim involving repeated measures ANOVA, with the effect size of $f=0.25$ for the Box and Block from our previous study, (Seo et al., 2014) a sample size of 19 is needed assuming a conservative correlation of 0.3 across evaluation times, for 80% power and 5% significance level. Thus, we will aim to obtain data from 24 participants. Considering that some may be found ineligible after enrollment, a total of 30 recruitment is proposed.
- Data sharing: Only de-identified coded data will be reported and/or shared with the public in publications, in ClinicalTrials.gov, or upon written request.

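### Durability is concluded from non-significant interactions that the power section never sizes; the stated N of 19 is not tied to any of the planned durability tests

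*Combined protocol and SAP*

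**What the plan says.** All of the following is in section 10.0 of the combined protocol and SAP unless noted.

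- **Power analysis.** The secondary ANOVA is sized "with the effect size of $f=0.25$ for the Box and Block from our previous study". The result is that "a sample size of 19 is needed assuming a conservative correlation of 0.3 across evaluation times"; power is set at 80% and the level at 5%. The effect tested, the number of measurements and any sphericity correction are not given. The target of 24 comes from the primary safety outcome.
- **Model.** Each hand function measure is analysed "with factors of vibration (on/off), condition (treatment/control), evaluation time (1-5), and their interactions". Section 1.0 gives the visits per condition as "for a total of 5 evaluations over 4 weeks", so there are ten evaluations over the two conditions.
- **Decision rule.** The first requirement is "A significant main effect of vibration, with improved hand function with vibration on vs. off". The rule then says that such a result, when combined "with non-significant interactions of vibration×evaluation time and vibration×condition, would indicate durability over a month". A significant interaction of either kind is read as desensitization.
- **Section 9.0, Durability,** describes a per-visit criterion: the instant effect should be present at every evaluation. Section 10.0 does not carry this into the formal rule.

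**The concern.** The rule has three parts: a 1-df main effect that must be significant, and a 4-df and a 1-df interaction that must not be. The main effect averages over visits, so it says little about whether the effect lasts. Only the interactions can show that it fades, and failing to detect them counts as support. The weaker those tests are, the more often the trial confirms its own hypothesis of no desensitization.

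A general statement of 80% power suggests that the secondary aim is adequately sized as a whole. If that figure does not cover the interactions, an effect that has gone by week 4 could still be reported as durable.

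**Working it through.** **1. Reproducing 19.** Inputs from the power analysis: f = 0.25, ρ = 0.3, α = 0.05, power 80%. For one within-subject factor with m levels, the noncentral F has λ = N·m·f²/(1−ρ), df1 = m−1 and df2 = (N−1)(m−1), with sphericity assumed.

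| Levels (df1) | Smallest N | Power at 19 | Power at 24 |
|---|---|---|---|
| 2 (1) | 46 | 41% | 51% |
| 5 (4) | 28 | 60% | 72% |
| 10 (9) | 19 | 81% | 91% |
| 20 (19) | 13 | 97% | 99% |

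For m = 10 and N = 19, λ = 19×10×0.0625/0.7 = 16.96 and power is 81.4% (78.6% at 18). The plan lists no 9-df test.

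**2. A second route to 19.** Read f = 0.25 as an on/off difference of 2×0.25 = 0.5 SD. With on–off correlation 0.3, a difference score has variance 2(1−0.3) = 1.4. Average ten of them, themselves correlated 0.3: 1.4×(1+9×0.3)/10 = 0.518. The standardized effect is 0.5/√0.518 = 0.695. A one-sample t test then has power 79.3% at 18, 81.7% at 19 and 90.3% at 24. This is the planned vibration main effect. A 20-cell omnibus test also gives 19 if epsilon is 0.5. None of these routes is an interaction.

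**3. Power of the interactions at n = 24.** Assumptions, which the documents do not supply: a 0.5 SD on/off effect, lost linearly over the five visits of the treatment month (0.5, 0.375, 0.25, 0.125, 0). Difference scores have variance v = 2(1−ρ_on-off) and common correlation r across visits.

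- *Vibration×time:* λ = n·S/[v(1−r)/2], df 4 and 92. S is the sum of squared deviations of the on/off profile averaged over the two months.
  - Loss in the treatment month only: the averaged profile runs from 0.5 to 0.25, S = 0.0391, λ = 24×0.0391/0.7 = 1.34, power 12%.
  - Loss in both months: S = 0.15625, λ = 5.36, power 40%.
- *Vibration×condition, loss in the treatment month only:* the monthly mean effects are 0.25 and 0.5. The standardized contrast is 0.25/√(2v(1−r)/5) = 0.25/√0.56 = 0.334, power 35%.

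| On–off correlation; r | V×time, treatment month only | V×condition, treatment month only | V×time, both months |
|---|---|---|---|
| 0.3; 0 | 12% | 35% | 40% |
| 0.3; 0.3 | 16% | 47% | 56% |
| 0.7; 0 | 24% | 67% | 80% |

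**4. The whole rule, loss in the treatment month only.** The main effect is then 0.375 on average. In the first row its standardized size is 0.375/√(1.4/10) = 1.00, power 99.7%. The three contrasts are orthogonal under this structure, so the chance of a durability conclusion is about 0.997×(1−0.123)×(1−0.348) = 57%. In the second row, main-effect power is 69% and the chance is 0.686×0.841×0.534 = 31%. In the third it is 1.000×0.758×0.332 = 25%. In each case the effect is zero at the last treatment visit.

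**The case against.** **The figure of 19 may be right for a planned test.** A reader might infer that 19 comes only from a ten-level omnibus test, or that it is an arithmetic error. Neither is supported. It reproduces exactly for the vibration main effect under step 2, and the power section describes its 0.3 as a correlation across evaluation times, which fits that reading. The extra on–off correlation is an assumption, but the documents do not rule it out.

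**Interaction power depends on unstated inputs.** This also stands. At on–off correlation 0.9 with r = 0, loss in the treatment month only gives λ = 24×0.0391/0.1 = 9.4 and 66% power for vibration×time. For vibration×condition it gives 0.25/√0.08 = 0.88 and about 98%. If f = 0.25 is assigned to vibration×time itself with all cells counted, power at 24 is about 97% or more. That last route is weak support. Section 2.0 describes the earlier studies as showing an instant effect and says durability is still to be studied, so they give no evident basis for the size of a change over weeks.

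**Section 9.0 already has a per-visit criterion.** True, and it points the right way. But section 10.0 states the formal rule without it.

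**The target is 24, not 19.** True, and nothing here calls for more participants.

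**Conclusion.** The point stands as a gap in specification and a flaw in the decision rule. The plan does not say what its 80% at 19 covers, and no reading found that gives 19 sizes the interactions on which durability partly rests.

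At the plan's f and 0.3 correlation, read as a 0.5 SD effect with on–off correlation 0.3, complete linear loss confined to the treatment month would be detected with about 12% to 16% power by vibration×time and 35% to 47% by vibration×condition. The rule would declare durability in roughly 31% to 57% of such trials. These figures rest on the assumed effect, loss pattern and correlations, and they improve markedly as the on–off correlation rises.

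A reader might go further and infer that the 80% claim is false for the durability tests, or that 24 is proven too few. The documents do not support that: the main effect is one of those tests, and with 24 it has about 90% power under step 2. What can be said is that the 80% is not shown to apply to the interactions. The primary safety sample size is unaffected.

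**What to change.** 1. **Section 10.0, Statistical analysis.** Do not conclude durability from non-significant interactions. Judge it from the on/off effect at the last visit of the treatment month and its change from the first visit, each with a confidence interval. This is consistent with the per-visit criterion in section 9.0. The interactions can stay as supporting tests.
2. **Section 10.0, Power analysis.** State the effect, number of measurements, correlation structure and sphericity assumption behind f = 0.25 and 19, and limit the 80% claim to that effect. Report power at 24 for each interaction over a stated range of correlations and loss patterns. Do not enter single fixed values. For example, over 99% for a constant 0.5 SD main effect needs uncorrelated difference scores; it is 90% at r = 0.3 and 76% at r = 0.5. Likewise 21% to 40% for vibration×time describes either the treatment month analysed alone (λ = 24×0.15625/1.4 = 2.68) or equal loss in both months.

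**Cost.** A revised paragraph in each place and a less favourable secondary claim; no extra participants. The intervals may be wide. With 24 participants the 95% half-width at the last visit is 2.069×√(v/24), which is 0.50 SD at on–off correlation 0.3 and 0.33 SD at 0.7. For the change from first to last visit with r = 0 it is 2.069×√(2v/24), or 0.71 and 0.46 SD. The result may therefore be inconclusive, and the plan should allow it to be reported as such.

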11.0 Provisions to Monitor the Data to Ensure the Safety of Subjects

- Data and Safety Monitoring Board (DSMB): The primary purpose of the DSMB is to ensure the safety of participants and the validity and integrity of data collected during the study. By having the DSMB, safety concerns will be addressed objectively, in a timely manner. If the intervention definitively has safety concerns, the DSMB may recommend stopping the study early.
- The DSMB will be composed of (1) a board certified physician with expertise in stroke management, (2) a registered and licensed occupational therapist with expertise in stroke rehabilitation, and (3) a biostatistician with expertise in design and analysis of clinical trials.
- The responsibilities of the DSMB are as follows. Prior to any enrollment, the DSMB will review the study design, protocol, recruitment/enrollment plan, statistical analysis plan, and data safety monitoring plan, and document the agreement or recommendation. Once the enrollment begins, the DSMB will convene every 3 months to review the safety data (i.e. worsening of hand sensation, hand strength, hand dexterity, upper limb pain level, upper extremity spasticity, and wrist skin irritation, and any other adverse events regardless of whether it is related to the device use or not) as well as the enrollment data including any discontinuation of participation in the study with or without adverse events, new enrollments, and progression of the enrollees' participation in the study. The DSMB will review the aggregated summary data as well as the individual participants' data (de-identified). The DSMB will provide recommendations for any adverse events and safety concerns. The DSMB will also provide a report to the IRB to summarize oversight activities, recommendations, and any concerns regarding participant safety.
- The DSMB will have access to coded (de-identified) data but not identifiable data. While the experimenters and participants are double-blinded to the condition assignment information during the study progression, the DSMB will have access to the condition assignment information during the study progression in order to assess

the safety of the TheraBracelet vibration in comparison to that of simply wearing a wristband (i.e. control) and separately assess other safety issues such as assessments.

- Reporting of safety data: All safety data including adverse events will be reported to the DSMB, IRB, and relevant funding agencies. Summative safety data will be reported in ClinicalTrials.gov and in publications. Following the guidelines, we will register this study in ClinicalTrials.gov as soon as the study commences (at the latest within 21 days after the first participant is enrolled) and report results including all adverse events as soon as the study is completed (at the latest within 12 months of the trial's primary completion date). To protect participants' confidentiality, personally identifiable information will not be used for reporting. Only de-identified or aggregated data will be used for reporting.
- Endpoint: Participants will be assured of their right to discontinue their participation in the study at any time. In addition, the study physician, [name], may recommend discontinuation of participation if his/her adverse event is deemed to warrant discontinuation, without breaking the double-blinding. However, the condition assignment information will be available to the DSMB to make appropriate judgment during the study progression.

12.0 Risks to Subjects

There is a slight risk for loss of confidentiality. There is a minor risk of physical and mental fatigue from engaging in the study activity. The treatment a person receives at one time point may be less beneficial than the other study treatment. There is a minor risk of skin irritation from wearing the wristband and/or from vibration. There is a minor risk of discomfort in moving the arm/hand due to the weight of the device on the wrist, although the device weighs only 40g. Potential risks that may be associated with use of wrist vibration all day every day for a month will be tested as the primary outcome measures of safety within the study. These risks are: deterioration of hand sensation, strength, and dexterity, increased upper limb pain level, spasticity level, and/or wrist skin irritation. Occurrence of these adverse events are expected to be rare because the intensity of vibration used in TheraBracelet is subliminal while we are exposed to higher-intensity, suprathreshold vibration daily (e.g. from a phone). TheraBracelet has also been used during hand task practices in chronic stroke survivors for a total of 6 hours over 2 weeks without reportable adverse events in the PI's current study. However, there has not been a study that focuses on safety of TheraBracelet. Currently there is no known information regarding any side effects associated with using this small imperceptible (unfelt) level of vibration all day every day for a month. Currently there is no vibration exposure guideline for this small level of vibration.

13.0 Potential Benefits to Subjects or Others

There may be no benefit from participating in this study. The potential benefit is that the vibration the person receives may help their hand function in daily living, although this cannot be guaranteed. The vibration the person receives may increase their innate hand function (without vibration) over time (assessed as secondary investigation under Secondary Aim), although this cannot be guaranteed. The knowledge regarding the potential of using unperceivable vibration as a daily assistive or therapeutic option is important to increase quality of life of people who had a stroke and may benefit stroke survivors in general. The risks are deemed reasonable in relation to the potential gain of knowledge regarding this technology's feasibility, safety, and efficacy in potentially enhancing hand function and quality of life.

14.0 Sharing of Data

The RESTORE registry (Pro#00037803), from which this study may recruit subjects, also serves as a data analysis tool by which interdisciplinary teams may share data across projects and provide MUSC's stroke recovery research community with a more complete registry with key stroke elements. Some subjects may have participated or will participate in other stroke related research studies at MUSC. Sharing data from this and other stroke research studies with RESTORE will allow for more targeted recruitment efforts in the future and could reduce the burden placed on subjects by reducing the duplicative efforts of collecting common data and physical function assessments requested by multiple studies and storing them in one centralized and secure location.

Subjects are informed in the consent process if they enroll into the RESTORE registry, their data from this study will be shared. Those who have participated in other stroke research will be asked to sign a Release of Study Records form to share data with RESTORE if they did not already authorize release. Subjects will be asked to sign a HIPAA authorization stating their health information may be disclosed to MUSC investigators requiring their data for their research projects upon approval by an Institutional Review Board.

